12.9	Protocol Deviations and Non-Compliance.....	47
12.10	Publication and Data Sharing Policy.....	48
12.11	Collaborative Agreements.....	48
12.12	Conflict of Interest Policy	49
13	Abbreviations.....	49
14	REFERENCES	50

Abbreviated Title: Burosomab for FD

Version Date: 02/20/2024

STATEMENT OF COMPLIANCE

The trial will be carried out in accordance with International Conference on Harmonisation Good Clinical Practice (ICH GCP) and the following:

- United States (US) Code of Federal Regulations (CFR) applicable to clinical studies (45 CFR Part 46, 21 CFR Part 50, 21 CFR Part 56, 21 CFR Part 312, and/or 21 CFR Part 812)

National Institutes of Health (NIH)-funded investigators and clinical trial site staff who are responsible for the conduct, management, or oversight of NIH-funded clinical trials have completed Human Subjects Protection and ICH GCP Training.

The protocol, informed consent form(s), recruitment materials, and all participant materials will be submitted to the Institutional Review Board (IRB) for review and approval. Approval of both the protocol and the consent form must be obtained before any participant is enrolled. Any amendment to the protocol will require review and approval by the IRB before the changes are implemented to the study. In addition, all changes to the consent form will be IRB-approved; an IRB determination will be made regarding whether a new consent needs to be obtained from participants who provided consent, using a previously approved consent form.

1 PROTOCOL SUMMARY

1.1 Synopsis

Title: A Phase 2 Study of Burosumab For Fibroblast Growth Factor-23 Mediated Hypophosphatemia in Fibrous Dysplasia

Study Description: This will be a phase 2, open-label, single-arm study to evaluate the safety and efficacy of burosumab to normalize serum phosphate levels in subjects with fibrous dysplasia (FD) and fibroblast growth factor 23 (FGF23)-mediated hypophosphatemia.

Objectives:

Primary Objective:

- Evaluate the efficacy of burosumab to normalize serum phosphate levels in subjects with FD and FGF23-mediated hypophosphatemia at 48 weeks.

Secondary Objectives:

- Evaluate the efficacy of burosumab to normalize serum phosphate levels in subjects with FD and FGF23-mediated hypophosphatemia at 24 weeks.
- Evaluate the safety and tolerability of burosumab in patients with FD.
- Evaluate the effect of burosumab on increasing serum phosphate and additional mineral markers.
- Evaluate the impact of burosumab on FD lesion activity.
- Evaluate the effect of burosumab on functional parameters.
- Evaluate the effect of burosumab on pain and health-related quality of life.

Endpoints:

Primary Endpoint:

- The proportion of subjects achieving serum phosphate levels within the target range (Z-score -1 to +2) at Week 48.

Secondary Endpoints:

- Proportion of subjects achieving serum phosphate levels within the target range (Z-score -1 to +2) at Week 24.
- Adverse events and clinical safety laboratory tests for up to 4 weeks after the final burosumab dose (48 weeks for adult subjects, 50 weeks for pediatric subjects).
- Change and percent change from baseline to post-baseline visits in serum phosphate, serum 1,25(OH)2D, ratio of renal tubular maximum reabsorption rate of phosphate to glomerular filtration rate (TmP/GFR).
- Change in FD lesion activity using 18F-NaF PET/CT total lesion activity from baseline to 48 weeks
- Change and percent change in serum bone turnover markers, including procollagen 1 N-terminal propeptide (P1NP), beta crosslaps C-telopeptides (CTX), osteocalcin, and bone-specific alkaline phosphatase from baseline to 48 weeks.
- Change in FD lesion histology and cell proliferation as assessed by minimally invasive bone biopsies from baseline to 48 weeks (adults with capacity to consent only) from baseline to 48 weeks
- Skeletal changes assessed on skeletal survey at baseline and 48 weeks
- Change from baseline to 48 weeks in:
 - Muscle strength

Abbreviated Title: Burosumab for FD

Version Date: 02/20/2024

- Range-of-motion
- Walking speed (9-minute walk)

Change from baseline to 48 weeks in patient reported outcomes measures:

- SF36: adults
- SF10: children
- PROMIS Pain Intensity: Pediatric and Parent Proxy version 1.0, Adult version 2.0
- PROMIS Pain Interference: Pediatric and Parent Proxy v 2.0, Adult v 1.1
- PROMIS Mobility: Pediatric and Parent Proxy version 2.0, Adult Mobility Lower Extremity v 1.0
- PROMIS Fatigue: Pediatric and Parent Proxy v 2.0, Adult FACIT 13a v1.0
- Activities of Daily Living Questions: adults and children

Study Population:

Up to 15 subjects with FD and FGF23-mediated hypophosphatemia

Phase:

2 National Institutes of Health (NIH) Clinical Center (CC)

Description of Sites/Facilities

Enrolling Participants:

Burosumab is an injectable solution in single use vials at concentrations of 30 mg/mL

Description of Study Intervention:

Estimated time from when the study opens to enrollment until completion of data analyses is approximately 20 months.

Study Duration:

Up to 50 weeks (2 week washout period + 48 week treatment period + final adverse event review)

1.2 Schema

NIH evaluation												NIH evaluation												NIH evaluation											
-2	0	2	4	6	8	10	12	14	16	18	20	22	24	26	28	30	32	34	36	38	40	42	44	46	48										
Washout period	Burosumab Treatment																																		
Subjects will be treated with burosumab for 48 weeks following a 2-week washout period. Evaluations will be performed at the NIH Clinical Center at baseline, 24, and 48 weeks. Between visits burosumab will be administered locally, and subjects will be monitored remotely with outpatient labs.																																			

1.3 Schedule of Activities (SoA)

Abbreviated Title: Burosumab for FD

Version Date: 02/20/2024

Procedures	Week 26	Week 28	Week 30	Week 32	Week 34	Week 36	Week 38	Week 40	Week 42	Week 44	Week 46	Week 48 Visit (NIH CC) ³	Week 50
Informed consent	-	-	-	-	-	-	-	-	-	-	-	-	-
Demographics	-	-	-	-	-	-	-	-	-	-	-	-	-
Medical history	-	-	-	-	-	-	-	-	-	-	-	X	-
Physical exam (including height, arm span, and weight)	-	-	-	-	-	-	-	-	-	-	-	X	-
Vital signs	-	-	-	-	-	-	-	-	-	-	-	X	-
Injection teaching	-	-	-	-	-	-	-	-	-	-	-	-	-
Functional parameters ⁴	-	-	-	-	-	-	-	-	-	-	-	X	-
NIH lab tests ⁵	-	-	-	-	-	-	-	-	-	-	-	X	-
Outpatient lab tests ⁶	-	X	-	X	-	X	-	X	-	X	-	-	-
Pregnancy test ⁷	-	X	-	X	-	X	-	X	-	X	-	X	-
Bone biopsy ⁸	-	-	-	-	-	-	-	-	-	-	-	X	-
Imaging assessment ⁹	-	-	-	-	-	-	-	-	-	-	-	X	-
Patient reported outcomes ¹⁰	-	-	-	-	-	-	-	-	-	-	-	X	-
Burosumab administration (pediatric subjects) ¹¹	X	X	X	X	X	X	X	X	X	X	X	-	-
Burosumab administration (adult subjects) ¹¹	-	X	-	X	-	X	-	X	-	X	-	-	-
Study close-out teleconference (pediatric subjects) ¹²												X	
Adverse event review and evaluation ¹²													

¹ Informed consent will be obtained by telephone or in person prior to the baseline visit.

² Subjects receiving supplemental phosphate, active vitamin D metabolites, or current burosumab treatment will discontinue these medications for 2 weeks prior to screening.

³ Visits will be conducted in the NIH Clinical Center in the inpatient, day hospital, or clinic settings as appropriate. All visits will occur within a window of +/- 5 days from the planned timepoint.

⁴ Muscle strength, range-of-motion, 9-minute walk test.

Abbreviated Title: Burosumab for FD

Version Date: 02/20/2024

⁵ Serum sodium, potassium, chloride, bicarbonate, glucose, blood urea nitrogen, creatinine, albumin, total protein, calcium, magnesium, phosphate, parathyroid hormone, 25-hydroxyvitamin D, 1,25-dihydroxyvitamin D, aspartate aminotransferase, alanine aminotransferase, total bilirubin, alkaline phosphatase, osteocalcin, procollagen type 1 N-terminal propeptide, Beta-CrossLaps C-telopeptides, intact FGF23 (baseline visit only), C-terminal FGF23 (baseline visit only), research blood, anti-drug antibodies, neutralizing antibodies (in samples testing positive for neutralizing antibodies only), and burosumab concentration. 24-hour urinary calcium, creatinine, phosphate (toilet trained subjects), random urinary calcium, creatinine, phosphate (non-toilet trained subjects), and TmP/GFR.

⁶ Serum calcium, phosphate, creatinine, and alkaline phosphatase. Random urine calcium, creatinine, and phosphate. Urine pregnancy test (girls and women of childbearing potential only). Outpatient labs will be obtained 3 +/- 2 days and reviewed prior to burosumab administration. Subsequent elements on the Schedule of Events will be dictated by the timing of the previous injection.

⁷ To be performed in girls and women of childbearing potential only. Female subjects of child-bearing potential must be non-pregnant and non-nursing. Additional pregnancy tests will be performed at any visit in which pregnancy status is in question. A serum pregnancy test will be performed in the event of a positive or equivocal urine pregnancy test result or can be performed if pregnancy test by urine is not feasible.

⁸ To be performed only in adult subjects with capacity to consent.

⁹ ¹⁸Sodium fluoride-PET/CT scan, skeletal survey, renal ultrasound. Will accept outside or internal imaging for ¹⁸Sodium fluoride-PET/CT scan, and/or skeletal survey as baseline study imaging if obtained within 6 months prior to Week 0/Baseline visit, as a means of reducing unnecessary repeated exposure to radiation

¹⁰ SF36 (adults), SF10 (children), PROMIS Pain Intensity (Pediatric and Parent Proxy version 1.0, Adult version 2.0), PROMIS Pain Interference (Pediatric and Parent Proxy v 2.0, Adult v 1.1), PROMIS Mobility (Pediatric and Parent Proxy version 2.0, Adult Mobility Lower Extremity v 1.0), PROMIS Fatigue (Pediatric and Parent Proxy v 2.0, Adult FACIT 13a v1.0), Activities of Daily Living Questionnaire (adults and children).

¹¹ Burosumab is administered every 2 weeks in children age <18 years, and every 4 weeks in adults age \geq 18 years. The initial dose will be administered at the NIH CC, and subsequent doses will be self/caregiver administered under the observation of the study team. If the target range is not reached for patients >18 year and older, dosing may be administered at every 2-week dosing intervals at the discretion of the PI.

¹² Final adverse event review will be performed 4 weeks +/- 5 days after the final dose: at the 48 week NIH CC visit for adult subjects, and at a teleconference at 50 weeks for pediatric subjects, or adult subjects who have been on every 2-week dosing interval.

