Multiple blood and urine collections will occur introducing known common risks (discomfort, bruising) for blood draws and/or intravenous catheter placement introducing smaller risks of complications including fainting (usually a vasovagal response to sight or insertion of needles) or inflammation of the insertion site (including potentially pain and swelling) and the potential for infection or venous thrombosis.

Bone biopsies in adult subjects may cause discomfort and pain for several days and can be treated safely with acetaminophen or more potent analgesics as needed. Bleeding and infection at the site of biopsy are possible but rare. Subjects may experience some transient anesthesia-related symptoms such as nausea, vomiting, decreased appetite, fatigue, and decreased blood pressure. Subjects may undergo a routine pre-anesthesia consult and be asked to sign a separate surgical consent form prior to the procedure. Only biopsies judged to be minimally invasive according to the judgement of the PI and surgeon will be performed. A bone biopsy will not be done if there is no site containing FD that allows a minimally invasive procedure with minimal risk of fracture.

At baseline and 48 weeks the following radiologic procedures will be performed: 1) ^{18}F Sodium fluoride-PET/CT scan to evaluate metabolic activity of FD lesions, 2) skeletal survey to include x-rays of the arms, legs, pelvis, skull, and lateral spine to evaluate for skeletal deformities and metaphyseal irregularities, and 3) CT-guided bone biopsy (adults with capacity to consent only). This radiation exposure is not necessary for medical care and is for research purposes only. The effective dose that participants will receive from participation in this research study is 2.1 rem for adults with capacity to consent; 1.7 rem for adults without capacity to consent, 1.8 rem for children ages 4-17; and 0.6 rem for children ages 1-4.

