3 OBJECTIVES AND ENDPOINTS

OBJECTIVES	ENDPOINTS	JUSTIFICATION FOR ENDPOINTS
Primary		
Evaluate the efficacy of burosumab to normalize serum phosphate levels in subjects with FD and FGF23-mediated hypophosphatemia at 48 weeks	The proportion of subjects achieving serum phosphate levels within the target range (Z-score -1 to +2) at Week 48	Serum phosphate is the primary driver of skeletal complications in patients with FGF23-mediated hypophosphatemia and has been correlated with poor clinical outcomes in patients with FD
Secondary		
Evaluate the efficacy of burosumab to normalize serum phosphate levels in subjects with FD and FGF23-mediated hypophosphatemia at 24 weeks	Proportion of subjects achieving serum phosphate levels within the target range (Z-score -1 to +2) at Week 24	Serum phosphate is the primary driver of skeletal complications in patients with FGF23-mediated hypophosphatemia and has been correlated with poor clinical outcomes in patients with FD

OBJECTIVES	ENDPOINTS	JUSTIFICATION FOR ENDPOINTS
Evaluate the safety and tolerability of burosumab in patients with FD	Adverse events and clinical safety laboratory tests for up to 48 weeks	Safety endpoints for expected and unexpected adverse events
Evaluate the effect of burosumab on increasing serum phosphate and additional mineral markers	Change and percent change from baseline to post-baseline visits in serum phosphate, serum 1,25(OH)2D, ratio of renal tubular maximum reabsorption rate of phosphate to glomerular filtration rate (TmP/GFR)	Safety endpoint for monitoring metabolic impact of burosumab in patients with FD
Evaluate the impact of burosumab on FD lesion activity	
 Change in FD lesion activity using 18F-NaF PET/CT total lesion activity from baseline to 48 weeks Change and percent change in serum bone turnover markers, including procollagen 1 N-terminal propeptide (P1NP), beta crosslaps C-telopeptides (CTX), osteocalcin, and bone-specific alkaline phosphatase from baseline to 48 weeks. Change in FD lesion histology and cell proliferation as assessed by minimally invasive bone biopsies from baseline to 48 weeks (adults with capacity to consent only) from baseline to 48 weeks Skeletal changes assessed on skeletal survey at baseline and 48 weeks. 	Safety endpoints to determine if burosumab impacts metabolic activity of FD lesions, which are a benign neoplastic process

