8.3.7 Bone Biopsy

Percutaneous core needle bone biopsies will be performed in adult subjects with capacity to consent at Weeks 0 and 48. Because FD is a benign neoplastic process, biopsies will be performed to evaluate for any potential deleterious effects of burosomab on FD tissue. This will include evaluation of tissue histology for changes in cell proliferation and neoplastic bone content. The first biopsy will be performed prior to burosomab therapy (baseline) and the second at the same site following completion of therapy (post treatment). The biopsies will be performed

by a licensed, credentialed practitioner in Interventional Radiology or the operating room of the NIH Clinical Center under local anesthesia with sedation. The biopsies will be performed from areas containing FD. The PI and the surgeon will jointly determine which sites are to be biopsied. All subjects will be evaluated by an anesthesiologist, who will determine the level of anesthesia needed based on clinical evaluation of the patient and planned procedure. Only biopsies judged to be minimally invasive (i.e. percutaneous procedures that allow bone to be removed via a core needle) will be performed. A bone biopsy will not be done if there is no site containing FD that allows a minimally invasive procedure with minimal risk of fracture.

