8.4.4 Time Period and Frequency for Event Assessment and Follow-Up

The occurrence of an adverse event (AE) or serious adverse event (SAE) may come to the attention of study personnel during study visits and interviews of a subject presenting for medical care, or upon review by a study monitor.

All AEs including local and systemic reactions not meeting the criteria for SAEs will be captured on the appropriate case report form (CRF). Information to be collected includes event description, time of onset, clinician's assessment of severity, relationship to study product (assessed only by those with the training and authority to make a diagnosis), and time of resolution/stabilization of the event. All AEs occurring while on study must be documented appropriately regardless of relationship. All AEs will be followed to adequate resolution.

Any medical condition that is present at the time that the subject is screened will be considered as baseline, recorded as patient medical history, and not recorded as an AE. However, if the subject's condition deteriorates at any time during the study, it will be recorded as an AE.

Changes in the severity of an AE will be documented to allow an assessment of the duration of the event at each level of severity to be performed. AEs characterized as intermittent require documentation of onset and duration of each episode. At each study visit, the investigator will inquire about the occurrence of AE/SAEs since the last visit. The study team will record all reportable events with start dates occurring any time after informed consent is obtained until 4 weeks after the last burosomab dose. Events will be followed for outcome information until resolution or stabilization.

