8.4.5 Adverse Event Reporting

Any untoward medical occurrences or unfavorable and unintended signs, symptoms, or diseases that occur in the pretreatment, treatment, or posttreatment period are to be considered AEs (and SAEs if appropriate), and consequently recorded and reported as such.

Subjects are to be queried regarding any AEs or SAEs at the time of each vital sign assessment, as well as at each visit, according to the Schedule of Activities (Section 1.3). Subjects will be asked to volunteer information with a nonleading question such as, "How do you feel?" Study center personnel will then record all pertinent information in the subject's CRF.

All AEs and SAEs reported by the subject (or subject's legal representative) or observed or otherwise identified by the investigator (or other study center personnel) at a defined study visit or during any communication with the subject (or subject's legal representative) occurring outside a defined study visit (from the time the subject signs the ICF to 30 ± 7 days after the last dose of burosomab) must be documented.

All AEs must be recorded on the appropriate AE reporting page of the subject's CRF whether or not they are considered causally related to the burosomab.

For every AE, the investigator must:

- Provide an assessment of the severity, causal relationship to burosomab, and seriousness of the event (i.e., whether it is a SAE)
- Document all actions taken with regard to burosomab
- Detail any other treatment measures taken for the AE
- Document resolution of the AE (with or without sequelae); ongoing; or lost to follow-up.

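### For adults who stay on 4-week dosing, the final adverse event review falls at the Week 48 biopsy visit, so delayed biopsy complications have no scheduled review

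*Combined protocol and SAP*

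**What the plan says.** **The biopsy.** Section 8.3.7: "Percutaneous core needle bone biopsies will be performed in adult subjects with capacity to consent at Weeks 0 and 48". The second is taken from the same site once therapy is complete. Section 2.3.1 warns that biopsies in adults "may cause discomfort and pain for several days" and lists bleeding and infection as possible but rare. Section 5.3.2 treats the biopsies as exceeding minimal risk with no prospect of direct benefit, and excludes adults without capacity from them.

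**The final review.** Footnote 12 in Section 1.3 sets it 4 weeks ± 5 days after the last dose: "at the 48 week NIH CC visit for adult subjects, and at a teleconference at 50 weeks for pediatric subjects". The rest of that sentence adds adults who have been on 2-week dosing to the Week 50 call. The endpoint text in Sections 1.1 and 9.1 agrees on 48 weeks for adults and 50 for children.

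**The recording window** is described in several ways:
- Section 8.4.4 records events with a start date "until 4 weeks after the last burosomab dose" and follows recorded events until they resolve or stabilize.
- Section 8.4.5 requires documentation, including of events raised outside visits, to "30 ± 7 days after the last dose of burosomab".
- The table in Section 3 has "Adverse events and clinical safety laboratory tests for up to 48 weeks".
- Section 4.1 describes a Week 50 final adverse event review and two-weekly evaluations through Week 50, with no limit by age or regimen.

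The 30-day telephone call in Section 7.2 is for subjects who terminate early, not for completers.

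**The concern.** Safety follow-up is tied to the last dose of burosumab, not to the last study procedure. For an adult on the default 4-week regimen the last procedure is an invasive research biopsy, done at the visit where scheduled adverse event review ends. A complication that appears some days later would be known only if the subject volunteers it, and under Section 8.4.4 it may fall outside the recording window even then.

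The two biopsies would also be observed unequally. The Week 0 biopsy is followed by weekly evaluations in weeks 1 to 4 (Section 4.1). Under footnote 12 the Week 48 biopsy is followed by none in these adults. The primary endpoint is not touched. What is at stake is the safety record of a procedure that carries risk and offers the subject no benefit.

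**Working it through.** **Inputs.** Day = 7 × week. In the Schedule of Activities the last adult dose on 4-week dosing is at Week 44. For adults on 2-week dosing I infer Week 46 from the pediatric row. The biopsy is at Week 48, and visits have a window of ± 5 days (footnote 3).

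**1. Reproduce the plan's own timing (footnote 12).**
- 4-week dosing: 7 × 44 = 308; 308 + 28 = day 336 = Week 48.
- 2-week dosing: 7 × 46 = 322; 322 + 28 = day 350 = Week 50.

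Both match the footnote.

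**2. Scheduled review after a biopsy on the nominal day (336).**
- 4-week dosing, footnote 12: 336 − 336 = 0 days.
- 2-week dosing, footnote 12: 350 − 336 = 14 days (9 to 19 with the ± 5 days on the review).
- 4-week dosing if Section 4.1 governs: 350 − 336 = 14 days.

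**3. Recording windows on 4-week dosing.**
- Section 8.4.4 ends on day 308 + 28 = 336.
- Section 8.4.5 ends on day 308 + 23 = 331 to 308 + 37 = 345, nominally 308 + 30 = 338.

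Days from biopsy to the end of the window (negative means it closes before the biopsy):

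| Biopsy day | 8.4.4 | 8.4.5 nominal | 8.4.5 range |
|---|---|---|---|
| 331 (visit 5 days early) | 5 | 7 | 0 to 14 |
| 336 (nominal) | 0 | 2 | −5 to 9 |
| 341 (visit 5 days late) | −5 | −3 | −10 to 4 |

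**4. Is there another scheduled contact?** The close-out teleconference row in the Schedule of Activities is labelled for pediatric subjects. The Section 7.2 call is for early terminators. Section 8.4.5 sets a documentation window but schedules no contact. Only Section 4.1 points to a Week 50 review for these adults, and it contradicts footnote 12 and Sections 1.1 and 9.1.

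**5. Would moving the call be enough?** A Week 50 call falls 350 − 308 = 42 days after a Week 44 dose. That is beyond 28 days (8.4.4) and beyond the latest limit of 37 days (8.4.5). The recording window must therefore be extended along with the call, or events reported at the call could be out of window.

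**The case against.** Several points on the other side are sound.

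- **Not all adults.** A reader who stops at the quoted part of footnote 12 might infer that every adult lacks later review. The rest of the sentence gives adults on 2-week dosing a Week 50 call, about 14 days after the biopsy. Adults without capacity, or with no suitable site, have no biopsy.
- **Not all complications.** One might infer that biopsy complications in general go uncounted. Procedural pain, sedation effects and immediate bleeding start on the day, at the NIH visit where the review is held, and Section 8.4.4 follows recorded events until they resolve or stabilize. Pain lasting several days is therefore captured at onset. If the visit runs late, Section 8.4.4 read literally has already closed, but the review at that visit would still find such events. The gap concerns delayed onset, and the protocol calls bleeding and infection rare.
- **Section 4.1 may be the intent.** If so, these adults do have a Week 50 review. That makes this partly a conflict to resolve. The adverse event row of the Schedule of Activities has no readable marks in the text available to me, so a row running to Week 50 cannot be ruled out.
- **A window tied to the last dose is coherent** for a safety endpoint about burosumab. It does not serve a research procedure performed when that window closes.

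What remains is that footnote 12, the most specific text, gives these adults no scheduled review after the biopsy, and the one section that does is in conflict with it.

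**Conclusion.** The point holds for adults with capacity to consent who are biopsied at Week 48 and have stayed on 4-week dosing. Under footnote 12 and the endpoint text they have 0 days of scheduled review after the biopsy; under Section 4.1 they would have 14. The Section 8.4.5 window nominally ends 2 days after the biopsy (−5 to 9 days on the nominal day; −10 to 14 across the visit window), with no contact scheduled to elicit events.

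This assumes that the Week 44 dose is given on its nominal day; an earlier last dose would close the windows sooner relative to the biopsy.

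Two further inferences are not supported. The share of biopsies affected cannot be stated: the documents give no number of adults, only a total of up to 15 subjects, and some adults may move to 2-week dosing. Nor does the 48-week wording in Section 3 show that pediatric events in Weeks 48 to 50 would be lost. Sections 1.1 and 9.1 and footnote 12 all carry children to Week 50, and Section 8.4.4 governs recording, so the Section 3 entry is an inconsistency of wording. The matter is worth correcting because the remedy is cheap, but it does not affect the efficacy analysis.

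**What to change.** 1. Amend footnote 12, and the label of the close-out teleconference row, so that any adult biopsied at Week 48 also has the existing Week 50 teleconference, with a direct question about the biopsy site.
2. Amend Sections 8.4.4 and 8.4.5 to use one post-dose window, and record adverse events to the later of the end of that window and the Week 50 call.
3. Carry the same window into Sections 1.1, 1.3, 3, 4.1 and 9.1. In Section 4.1, say explicitly which subjects have the Week 50 review.

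The cost is one phone call per biopsied adult on 4-week dosing, in a trial of at most 15 subjects, using a contact already in the schedule, plus the wording changes. No visit or laboratory test is added.
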